10.4. Contraceptive Guidance and Collection of Pregnancy Information Definitions

Woman of Childbearing Potential

A woman is considered fertile following menarche and until becoming postmenopausal unless permanently sterile (see below).

Women in the Following Categories are Not Considered Women of Childbearing Potential

- 1. Premenopausal female with 1 of the following:
 - Documented hysterectomy
 - Documented bilateral salpingectomy
 - Documented bilateral oophorectomy
 - Note: Documentation can come from the site personnel's review of the subject's medical records, medical examination, or medical history interview.

2. Postmenopausal female

- A postmenopausal state is defined as no menses for 12 months without an alternative medical cause. A high follicle stimulating hormone (FSH) level in the postmenopausal range, as per local laboratory reference ranges, will be used to confirm a postmenopausal state in women not using hormonal contraception or hormonal replacement therapy (HRT). However, in the absence of 12 months of amenorrhea, a single FSH measurement is insufficient.
- Female subjects on HRT and whose menopausal status is in doubt will be required to use one of the non-estrogen hormonal highly effective contraception methods if they wish to continue their HRT during the study. Otherwise, they must discontinue HRT to allow confirmation of postmenopausal status before study enrollment.

Pregnancy Testing

• Women of childbearing potential should only be included after a negative serum pregnancy test. Additional pregnancy testing should be performed per the time points specified in the Schedule of Activities (Table 1 and Table 2).

Collection of Pregnancy Information

- Pregnancy data will be collected during this study for all subjects and a female spouse/partner of male subjects. Exposure during pregnancy (also referred to as exposure in utero) can be the result of either maternal exposure or transmission of drug product via semen following paternal exposure.
- If a female subject participating in this study or a male subject's female sexual partner of childbearing potential becomes or is found to be pregnant while being treated or exposed to study drug, the Investigator must submit the "Pregnancy Reporting and Outcome/Breast Feeding Form" to the Sponsor or designee via the same method as SAE reporting. (Section 10.3). When the outcome of the pregnancy becomes known,

- the form should be updated and submitted to the Sponsor's Global Drug Safety (GDS). If additional follow-up is required, the Investigator will be requested to provide the information.
- Exposure of an infant to an Alexion product during breastfeeding must also be reported (via the "Pregnancy Reporting and Outcome Form/Breastfeeding" form) and any AEs experienced by the infant must be reported to the Sponsor's GDS or designee via facsimile or email (Section 10.3).
- A pregnancy in itself is not regarded as an AE unless there is a suspicion that the study drug may have interfered with the effectiveness of a contraceptive medication. However, complications of pregnancy and abnormal outcomes of pregnancy are AEs and may meet the criteria for an SAE (eg, ectopic pregnancy, spontaneous abortion, intrauterine fetal demise, neonatal death, or congenital anomaly). Elective abortions without complications should not be reported as AEs (Section 8.3.5).

10.5. Abbreviations

A list of abbreviations and terms are used in this study protocol is provided in Table 11.

Table 11: List of Abbreviations and Definitions of Terms

Abbreviation	Definition	
λ_z	apparent terminal-phase elimination rate constant	
%CV	arithmetic coefficient of variation	
AE	adverse event	
ALT	alanine aminotransferase	
ANOVA	analysis of variance	
AST	aspartate aminotransferase	
AUC	area under the plasma concentration versus time curve	
AUCt	area under the plasma concentration versus time curve from time 0 to the last quantifiable concentration	
AUC_{∞}	area under the plasma concentration versus time curve from zero to infinity	
CL/F	clearance/bioavailability	
C_{max}	maximum observed concentration	
CONSORT	Consolidated Standards of Reporting Trials	
Ср	ceruloplasmin	
СрС	ceruloplasmin-bound copper	
CRF	case report form	
CRU	clinical research unit	
CTCAE	Common Terminology Criteria for Adverse Events	
Cu	copper	
CV	coefficient of variation	
DAP	data analysis plan	
EC	enteric-coated	
EOS	End of Study	
ET	Early Termination	
FSH	follicle-stimulating hormone	
GCP	Good Clinical Practice	
GI	gastrointestinal	
GDS	Global Drug Safety	
HBsAg	hepatitis B surface antigen	
HCV	hepatitis C virus	
HIPAA	Health Insurance Portability and Accountability Act	
IB	Investigator's Brochure	
ICF	informed consent form	
IEC	Independent Ethics Committee	
MELD	model for end-stage liver disease	

Mo	molybdenum
NCC	non-ceruloplasmin-bound copper
NCC _{corrected}	corrected NCC
PD	pharmacodynamic(s)
PK	pharmacokinetic(s)
PPI	proton pump inhibitor
PUF	plasma ultrafiltrate
QT	interval between the start of the Q wave and the end of the T wave in an ECG
QTcF	QT interval corrected using the Fridericia's formula
RR	respiratory rate
SAE	serious adverse event
SAP	Statistical Analysis Plan
TEAE	treatment-emergent adverse event
TESAE	treatment-emergent serious adverse event
t _{1/2}	terminal elimination half-life
t _{max}	time to maximum concentration
TPC	Cu-tetrathiomolybdate-albumin tripartite complex formed after ALXN1840 administration
UC	uncoated capsules
ULN	upper limit of normal
UWDRS	Unified WD Rating Scale
V _d /F	apparent volume of distribution
WD	Wilson disease

1. INTRODUCTION

The purpose of this Statistical Analysis Plan (SAP) is to define the variables and analysis methodology to address the study objectives.

The protocol dated 09 Apr 2019, Amendment 1, was used in the preparation of this SAP.

Pharmacokinetic (PK) parameters calculations and statistical analyses will be the responsibility of Richmond Pharmacology Ltd (RPL). Tables, figures, and listings (TFLs) will be produced using Statistical Analysis Software (SAS), Version 9.3 or higher.

2. STUDY OBJECTIVES AND ENDPOINTS

2.1 Study objectives

The objectives of this study are:

Primary

 To assess the relative bioavailability of ALXN1840 administered orally as 3 × 5 mg enteric-coated (EC) tablets (test) versus 1 × 15 mg EC tablet (reference).

Secondary

To assess the overall safety and tolerability of ALXN1840.

Exploratory

- Relationships between Clearance/bioavailability (CL/F) and body size, body weight (kg) and body mass index (BMI kg/m²).
- To explore pharmacodynamics (PD) and biomarkers of 15 mg ALXN1840 among the following dosing regimens: either as a single 15 mg EC tablet (Treatment A) or 3 EC tablets of 5 mg (Treatment B).

2.2 Endpoints

Primary

• PK parameters for plasma total molybdenum (Mo) including the maximum observed plasma concentration (C_{max}), the area under the plasma concentration versus time curve from zero to the last quantifiable concentration (AUC_t), and extrapolated to infinity (AUC_{∞}).

Secondary

 Safety assessed by incidence of treatment emergent adverse events (TEAEs) and serious TEAEs (TESAEs), physical examination, vital signs measurements, clinical laboratory, and 12-lead electrocardiogram (ECG) results.

Exploratory

- CL/F, body weight, and body mass index.
- Absolute and percent changes of plasma copper (Cu) levels including total Cu, ceruloplasmin (Cp), ceruloplasmin-bound copper (CpC) and nonceruloplasmin-bound copper (NCC).
- The NCC level will be corrected for the amount of Cu bound to the TPC resulting in corrected NCC (NCC_{corrected}).

3. STUDY DESIGN

This is a single-center, randomized, open-label, 2-way crossover study to assess the single-dose pharmacokinetics (PK) of ALXN1840 EC tablets at 2 dose strengths in healthy male and female adult subjects under fasting conditions. Pharmacokinetic parameters will be calculated based on the measurement of plasma total Mo concentration. A total of 48 healthy, adult participants (20-28 male and 20-28 female) who complete the study screening assessments and meet all eligibility criteria will be enrolled to allow for a minimum of 40 subjects to complete the study (20-24 subjects in each sequence, 10-14 of each sex in each sequence).

3.1 Overall Design

The study has a Screening Period (Days -28 to -2), 2 Dosing Periods (Day -1 to Day 11 each) and an end-of-study (EOS) visit 14 days (+2 days) post final dose. After completing the Screening Period, enrolled subjects will be admitted to an inpatient facility (Clinical Research Unit [CRU]) on Day -1 for dosing on Day 1 in Dosing Period 1. Subjects will be readmitted to the CRU for Dosing Period 2 following a minimum of 14 days after the previous dose. In each Dosing Period, subjects will receive 1 of the 2 treatments as illustrated below:

Treatment A (reference)	1 x 15 mg ALXN1840 EC tablet
Treatment B (test)	3 x 5 mg ALXN1840 EC tablets

Table 1: Treatments

Subjects will return to the CRU 14 days (+2 days) after the final dose of study drug for the EOS visit with follow-up procedures, and to determine if any adverse event (AE) has occurred since the last study visit. If subjects withdraw from the study early, they will be seen and assessed by the Investigator, whenever possible, to undergo the procedures associated with the EOS visit.

Subjects may be replaced at the discretion of the Sponsor.

A total of 48 subjects will be enrolled (20-28 male subjects and 20-28 female subjects) to ensure a minimum sample size of 40 subjects (20-24 subjects in each sequence, 10-14 of each sex in each sequence) complete the study.

Each subject will receive both treatments in 1 of the 2 sequences as defined in the table below according to the study drug dosing regimen outlined above, where the single 15 mg EC tablet (Treatment A) is the "reference" dose and the 3 EC tablets of 5 mg (Treatment B) are the "test" dose.

Sequence	Treatment	Sequence	Male	Female	Total
Number	Period 1	Period 2			
1	Α	В	10-14	10-14	24
2	В	А	10-14	10-14	24
Total			20-28	20-28	48

Table 2: Treatment Sequence

3.2 Duration of Study

The planned study duration is approximately 70 days; up to 27 days for screening, approximately 29 days for dosing and follow-up, and an interval of at least 14 days between the 2 Dosing Periods.

[figure not shown]

Figure 1: Study ALXN1840 Schematic

- * Subjects will leave the Clinical Research Unit on Day 11 of Dosing Period 1 and will be readmitted following a minimum of 14 days after the dose of study drug for Dosing Period 2.
- ** EOS visit to be performed 14 days (+2 days) after the final dose of study drug. Abbreviations: EOS = end of study, PD = pharmacodynamics; PK = pharmacokinetics.

3.3 Sample size

The study sample size is not based on hypothesis testing with statistical considerations. A sample size of 40-48 subjects (20-24 subjects in each sequence; 10-14 male and female subjects in each sequence, with a maximum split in either direction of approximately 60%:40%) has been selected based on practicality and convention for this type of study. Considering potential for subject drop-out of the study, a total of 48 subjects will be enrolled with 20-28 male subjects and 20-28 female subjects.

3.4 Randomization and Blinding

This is an open-label study where, in order to minimize selection bias in treatment assignment, subjects will be randomized to 2 treatment sequences.

- Eligible subjects who meet all inclusion and no exclusion criteria will be assigned unique numbers for enrollment.
- Study subject numbers will not be reallocated once assigned.
- To achieve balance between the number of males and females in the 2 treatments sequence the maximum split in either direction will be approximately 60%:40% (10-14 of each sex in each sequence).
- Subjects randomized to Treatment A will receive 1 x 15 mg ALXN1840 EC tablet, whilst subjects randomized to Treatment B will receive 3 x 5 mg ALXN1840 EC tablets.

4. STATISTICAL ANALYSES

In general, descriptive statistics for continuous variables will include number of non-missing values (n), arithmetic mean, standard deviation (SD), median, minimum, and maximum.

Descriptive statistics for PK parameters will include number of non-missing observations (n), arithmetic mean, SD, arithmetic coefficient of variation (CV), geometric mean, geometric CV, median, minimum and maximum.

Categorical variables will be summarized using frequency counts and percentages.

For all tables, except PK parameter tables, descriptive statistics for minimum and maximum will be presented with the same decimal digits as the original data, and with 1 more decimal place than the original data for mean and median; SD will be reported with 2 more decimal places than the original data. Descriptive statistics and percentages and frequency counts will be summarized by sex, treatment, period and sequence, where appropriate.

PK parameters will be presented as follows in the listing: C_{max} and time to maximum observed plasma concentration (T_{max}) will be presented as given in the raw data; AUC_t , AUC_{∞} , the apparent terminal-phase elimination rate constant (λ_z) , the terminal elimination half-life $(t_{1/2})$, CL/F, and the apparent volume of distribution (Vd/F) will be presented with 3 decimal places. Descriptive statistics for PK parameters will be presented with decimal places as appropriate for the parameter and treatment.

The analyses will be presented by treatment, sex, period and sequence where appropriate. All collected data will be presented in by-subject listings. Listings will be ordered by treatment sequence and subject number and will include all randomized subjects.

Baseline will be defined as the last non-missing value among assessments recorded prior to first administration of study drug per period, where unscheduled assessment at the respective scheduled study are also taken into account. Changes from baseline values will be calculated as the post-baseline assessment value minus the baseline value per period. In general, only observed values from scheduled time points will be used to create summary tables, with the exception of unscheduled assessments on the respective study day. It is assumed that unscheduled assessments on scheduled study days are repetitions of potentially invalid scheduled assessments, and thus those unscheduled assessments will replace the respective scheduled assessments for summary tables and further statistical analyses.

Early Termination (ET) visits will be recoded to ET visits where necessary and reported as ET.

Deviations from the planned analyses will be described in the final clinical study report (CSR).

Page layout of the TFLs will be in landscape mode and will be provided as RTF files in Microsoft Word. Final TFLs will additionally be created in bookmarked portable document format (PDF). Further details of page layout will be provided in the TFL shell document.

All statistical analyses will be conducted using SAS® for Windows® Version 9.3 or higher.

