8.2.4. Clinical Safety Laboratory Assessments

All protocol-required laboratory assessments, as defined in Section 10.2, must be conducted in accordance with the Schedule of Activities (Table 1 and Table 2) and the laboratory manual. Clinical and laboratory assessments will be performed by a local laboratory to assess safety of ALXN1840. Laboratory assessments will include full liver safety tests, creatinine, and calculation of creatinine clearance.

• The Investigator must review the laboratory report, document this review, and record all clinically relevant changes occurring during the study in the AE section of the CRF. The laboratory reports must be filed with the source documents.

- All laboratory tests with values considered clinically significantly abnormal during
 participation in the study will be repeated until the values return to normal or baseline
 or are no longer considered clinically significant by the Investigator or medical
 monitor.
 - If such values do not return to normal/baseline within a period of time judged reasonable by the Investigator, the etiology should be identified, and the Sponsor's medical monitor should be notified.
 - If laboratory values from non-protocol-specified laboratory assessments
 performed at the institution's local laboratory require a change in subject
 management or are considered clinically significant by the Investigator (eg, SAE
 or AE or dose modification), then the results must be recorded in the CRF.
- The maximum amount of blood to be collected from each subject over the duration of the study, including any extra assessments that may be required, will not exceed 500 mL. Repeat or unscheduled samples may be obtained for safety and/or eligibility reasons or if there are any technical issues with the samples. Please refer to the laboratory manual for specific details regarding plasma sampling volumes.

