10.2. Clinical Laboratory Tests

The tests detailed in Table 10 will be performed by the local laboratory.

• Protocol-specific requirements for inclusion or exclusion of subjects are detailed in Section 5 of the protocol.

• Additional tests may be performed at any time during the study as determined necessary by the Investigator or required by local regulations. Investigators must document their review of each laboratory safety report and indicate whether out of range results are clinically significant ("CS") or not clinically significant ("NCS").

Table 10: Protocol-Required Safety Laboratory Assessments

Laboratory	Parameters			
Assessments				
Hematology	Platelet count	RBC indices:	WBC count with differential:	
	RBC count	Mean corpuscular volume	Neutrophils	
	Hemoglobin	Mean corpuscular	Lymphocytes	
	Hematocrit	hemoglobin	Monocytes	
		% Reticulocytes	Eosinophils	
			Basophils	
Clinical	BUN	AST	Total and direct bilirubin	
chemistry	Chloride	ALT	Total protein	
-	Potassium	Alkaline phosphatase,	Albumin	
	Bicarbonate	Gamma glutamyltransferase	Creatinine	
	Sodium	HbA1C (Screening only)	Creatine phosphokinase	
	Glucose	Urea		
Coagulation	International normalized ratio	, partial thromboplastin time, pr	othrombin time	
Routine	Specific gravity, pH, glucose, protein, blood, ketones, bilirubin, urobilinogen, nitrite,			
urinalysis	leukocyte esterase			
		any leucocytes, more than a trac-	e protein, nitrites, and blood [if	
	not menstruating] are abnorm	,		
Other screening	 Alcohol breath and urine drug screen (to include at minimum: amphetamines, 			
tests	barbiturates, benzodiazepines, cocaine, opiates, phencyclidine, methamphetamin			
		methamphetamine, methadone,	and tetrahydrocannabinol	
	[cannabinoids])			
	Cp and Cu concentra			
		tibodies, HBsAg, anti-HBC IgC	G + IgM (if IgG positive), and	
		rmation by HCV RNA		
	1 0	cy test (as needed for women of	childbearing potential)	
	FSH (postmenopaus)	al females only)		

Abbreviations: ALT = alanine aminotransferase; AST = aspartate aminotransferase; BUN = blood urea nitrogen; Cp = ceruloplasmin; Cu = copper; FSH = follicle stimulating hormone; HBsAg = hepatitis B surface antigen; hCG = human chorionic gonadotropin; HCV = hepatitis C virus; RBC = red blood cells; WBC = white blood cells.

10.3. Adverse Events: Definitions and Procedures for Recording, Evaluating, Follow-up, and Reporting

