4.11.2 Laboratory Data

Clinical laboratory parameters (including blood chemistry, haematology, coagulation, urinalysis and other laboratory results) will be listed and abnormal parameters will be flagged as high (H) or low (L) according to reference ranges. Absolute (observed) values and changes from baseline (continuous variables) will be summarized for each parameter and scheduled time point by treatment. The last lab value will be used for summary analysis if repeated measurements are made at any time point.

For summary statistics, a lab value with "<" will be replaced with a numeric value by removing the "<" sign. In the listings, the values will be displayed as originally reported by the laboratory.

Laboratory parameter values will be graded according to the Common Terminology Criteria for Adverse Events (CTCAE) and summarized by CTCAE grade. Non-protocol parameters will only be listed, in a separate listing, if required. Shift tables by treatment will be produced for all other laboratory parameters. These tables will summarize the number of subjects with each baseline grade relative to the normal ranges and changes to the worst highest grade assessed post-dose during the study. Similarly, shift tables from baseline based on NCI toxicity grade will be created.

As per the study protocol, any laboratory tests with values considered clinically significantly abnormal are to be repeated until the values return to normal or baseline or are no longer considered clinically significant by the Investigator or medical monitor. For all summary analyses, only the last available of all repeated measurements is to be used.

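### The SAP does not reconcile its scheduled-time-point, same-day replacement and last-repeat rules with the worst-post-dose-grade laboratory tables, and applying any of them there can understate the worst grade

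*SAP*

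**What the plan says.** Four provisions bear on which laboratory values reach the worst-grade tables.

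- **Restriction (SAP 4).** As a general default, "only observed values from scheduled time points will be used to create summary tables, with the exception of unscheduled assessments on the respective study day". No table is named as exempt.
- **Same-day replacement (SAP 4).** Extra values on a scheduled day are presumed to be repeats of possibly invalid results, so "those unscheduled assessments will replace the respective scheduled assessments for summary tables and further statistical analyses".
- **Last repeat (SAP 4.11.2).** "For all summary analyses, only the last available of all repeated measurements is to be used".
- **Worst grade (SAP 4.11.2).** The shift tables show, by treatment, baseline grade against "changes to the worst highest grade assessed post-dose during the study". Protocol 9.4.2 uses the same words. SAP 4.11.2 also asks for a second set of shift tables on NCI toxicity grade and for summaries by CTCAE grade.

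The protocol expects values outside the schedule. Under Protocol 8.2.4, tests judged abnormal to a clinically significant degree "will be repeated until the values return to normal or baseline" or lose their clinical significance. Protocol 10.2 adds: "Additional tests may be performed at any time during the study as determined necessary".

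**The concern.** The first three rules suit tables of means by visit, where each subject should contribute one value per time point. A worst-grade table has a different purpose: it should find the most extreme value, whenever it was taken. The SAP does not say that the rules stop at the by-visit tables. Two competent programmers could therefore produce different shift tables from the same data and both claim to have followed the plan.

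The possible loss is not random. Values taken off schedule or as repeats come mainly from subjects who already had an abnormal result. Safety and tolerability form the secondary objective, and clinical laboratory results are one of its endpoints. Protocol 2.3.1 names transaminase rises, thrombocytopenia, neutropenia and anemia as the findings relevant to these volunteers, and all of them are graded from laboratory data.

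**Working it through.** No figure in the plan needs reproducing here. The check is a count of sampling days and a side-by-side application of the rules.

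**Step 1: where off-schedule values can fall.** Protocol Table 2 schedules post-dose chemistry and hematology on Day 1 (4 h), Day 2 (24 h), Day 5 (96 h) and Day 10 (216 h). Subjects leave the unit on Day 11.

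- Days 1 to 11 with no scheduled chemistry or hematology sample: 3, 4, 6, 7, 8, 9 and 11, so 11 − 4 = 7 of 11.
- Coagulation and urinalysis are not sampled on Day 10, so 11 − 3 = 8 of 11.
- Gaps between scheduled post-dose chemistry and hematology samples: 24 − 4 = 20 h, 96 − 24 = 72 h and 216 − 96 = 120 h. The longest is 120 h.

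**Step 2: direction.** Let S be all of a subject's post-dose grades in a period. Each rule keeps a subset T of S, and max(T) ≤ max(S) always. Against the full set, no rule can raise the worst grade, and each can lower it.

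**Step 3: invented grade sequences, not trial data.** Days 1 and 2 are grade 0 throughout.

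| Case | Later grades | SAP 4 restriction and replacement | SAP 4.11.2 last repeat | All post-dose values |
|---|---|---|---|---|
| a | Day 5: 1; unscheduled Day 7: 3; Day 10: 1 | 1 | 3 if Day 7 counts as a repeat of Day 5 | 3 |
| b | Day 5: 3, same-day repeat: 1; Day 10: 0 | 1 | 1 | 3 |
| c | Day 5: 3; repeats Day 6: 2 and Day 7: 0; Day 10: 0 | 3 | 0 | 3 |

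Case a shows the restriction dropping an off-schedule worst value. Case b shows that a worst grade on a scheduled day can also go, through replacement. Case c shows the same through the last-repeat rule.

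Cases a and c also show the rules pulling in opposite directions. In a, the last-repeat rule may admit a value that Section 4 shuts out. In c, it removes a value that Section 4 keeps. The result depends on which sentence the programmer applies.

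**Step 4: size per subject.** If all 48 subjects receive a treatment, one misplaced subject moves that column by 1/48 = 2.1%.

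**The case against.** The strongest reply is that the SAP already resolves the matter. The Section 4 sentence is only a general default, while the shift-table sentence is specific and names no visit limit. On ordinary reading the specific sentence governs, so it can itself be the exception to the restriction. This has force: a reader might infer that the SAP definitely excludes off-schedule values from the shift tables, and the documents do not support that. However, the last-repeat sentence stands in the same section as the shift-table definition and applies to every summary analysis, so specificity does not settle that conflict.

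A second reply is that nothing is lost. SAP 4 lists all collected data, and SAP 4.11.2 flags values outside the reference range. Protocol 10.3.1 makes laboratory abnormalities adverse events when the investigator judges them clinically significant, and SAP 4.11.1 tabulates treatment-emergent events by treatment and worst toxicity. This also stands. A reader might infer that a serious laboratory excursion could vanish from the safety results, and that is not supported. What remains is that listings give no counts by treatment, and that adverse-event capture depends on the investigator's judgement whereas grading does not.

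Third, Protocol 2.3.1 says potential drug effects appeared only after several weeks of daily dosing in patients, and here each volunteer receives two single doses. That supports expecting few affected subjects.

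**Conclusion.** The point holds as an unresolved conflict between rules. If any of the three selection rules is carried into the worst-grade tables, the reported worst grade can only fall or stay the same, and the subjects exposed are mainly those whose abnormality was followed up. The reach is limited to the CTCAE-grade summaries and both sets of shift tables. Listings and adverse-event tables keep the clinically significant findings, the safety analysis is descriptive, and the primary bioavailability analysis is untouched.

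The number of subjects affected is probably small and cannot be estimated from the documents. A reader might turn the 7 of 11 unsampled days into a probability that a peak is missed. That would need daily follow-up sampling and a peak day unrelated to the schedule, and the documents support neither: repeats follow an abnormal result, often a scheduled one already eligible for the table, and a missed value matters only if it carries a higher grade. The day count is context only.

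**What to change.** In SAP 4 and 4.11.2, state that the scheduled-time-point restriction, the same-day replacement rule and the last-repeat rule apply only to summaries by time point. In 4.11.2, add that the CTCAE worst-grade summaries and both sets of shift tables use all valid post-dose values in each period: scheduled, unscheduled and repeat, including those from days with no scheduled sample. Leave out only results documented as invalid.

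All three rules need the limit. Changing the Section 4 restriction alone would leave the replacement and last-repeat sentences contradicting the new text.

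The cost is a few sentences in the SAP and a small programming change, with no new data. One small downside is that subjects who are retested more often have more chances to show a worse grade; a footnote to the tables can say so.
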